- 3. The study-specific criterion for permanent discontinuation from study treatment for hypertension is very conservative, i.e., discontinuation from study as soon as mean SBP is ≥ 180 and/or mean DBP is ≥ 110 mmHg. This criterion has been changed to allow for confirmation of the values by a second BP measurement. If the second measurement confirms the value (i.e., mean SBP ≥ 180 and/or mean DBP ≥ 110 mmHg) the subject must be permanently discontinued from study treatment.
- 4. The sample size for this study assumed a standard deviation (SD) for the primary endpoint (change from baseline to Week 8 in mean trough SiDBP, measured by OBPM) of 9 mmHg, based on several published studies using conventional office BP devices. With BpTRU the variability may be lower. For this reason, the SD of the primary endpoint will be estimated in a blinded fashion based on the first 100 randomized subjects and the sample size will be adjusted accordingly, while also taking into consideration the need for sufficient exposure to allow proper evaluation of the safety of the compound (e.g., fluid retention) in this indication. The number of randomized subjects is expected to be between 300 and the originally planned 540.

Additional changes have been made in order to allow more flexibility before and during the screening procedure (i.e., possibility for subjects without a confirmed diagnosis of

Essential hypertension Protocol AC-080A201 Version 3 30 May 2016, page 18/112

Confidential

hypertension to undergo a pre-screening process to confirm the diagnosis of hypertension before entering the study).

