Aminotransferases, total and direct bilirubin, and alkaline phosphatase levels must be monitored weekly after study drug discontinuation until values return to pre-treatment levels or within normal ranges.

Other diagnoses (e.g., viral hepatitis, mononucleosis, toxoplasmosis, cytomegalovirus) and/or etiologies (e.g., acetaminophen-related liver toxicity) should be considered and ruled out by performing the appropriate tests.

All liver aminotransferases abnormalities leading to study drug interruption or discontinuation must be recorded as AEs [see Section 10].

An ILSDRB provides ongoing assessment and advice regarding any hepatic events that may require further evaluation during the study.

To ensure the proper and comprehensive evaluation of hepatic events, additional subject data might be collected via Actelion Global Drug Safety.

D) Hemoglobin abnormalities

In the event of hemoglobin decrease from baseline* of > 20 g/L, a hemoglobin retest must be performed within 10 days, with additional laboratory evaluations that may include, but are not limited to, any of the following:

 Red blood cell cellular indices (mean corpuscular volume, mean corpuscular hemoglobin, mean corpuscular hemoglobin concentration), peripheral blood smear, reticulocyte count, iron status (iron level, serum ferritin, total iron binding capacity, transferrin saturation), lactate dehydrogenase (LDH), indirect bilirubin.

Study drug should be stopped if clinically mandated based on the investigator's judgment, or in any of the following situations:

- A decrease in hemoglobin to < 80 g/L (< 4.9 mmol/L),
- A decrease in hemoglobin from baseline of > 50 g/L,
- The need for transfusion.

E) Initiation of forbidden medications

Study treatment must be permanently discontinued if any forbidden therapy as listed in Section 5.2.4 is started during the study.

^{*} Baseline hemoglobin: last value obtained prior to first intake of DB study treatment.

Essential hypertension Protocol AC-080A201 Version 3 30 May 2016, page 52/112

Confidential

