9.1 Missing data

All analyses based on the PPS will be based on observed cases (OC). It is acknowledged that the PPS analyses are based on a selected subset of patients who completed the 8 weeks of DB treatment with sufficient compliance and who have no missing data at Week 8. For the assessment of dose-response reliance on this subset was deemed appropriate.

In analyses based on the FAS missing data will be imputed using last observation carried forward (LOCF). This may be justified as a conservative analysis since in this study the majority of patients are expected to improve over time [EMA 2010].

Baseline observation carried forward (BOCF) will be used as a sensitivity analyses for missing data imputation. Another sensitivity analysis is provided by a mixed model which does not impute the missing data and, in that sense, can be seen as a OC analysis. Mixed models are based on the missing at random (MAR) assumption, i.e.: missing data can be fully accounted for by baseline covariates and prior measurements. The MAR assumption is not unreasonable in the hypertension context, although it cannot be proven.

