10.2 General rules for data presentations

This section describes the general rules applied for all data displays.

SAS version 9.3 is used for the statistical analyses except for the primary endpoint (dose-response analysis) that is analyzed by means of the R package.

Unless otherwise specified in this document:

- All listings are sorted by randomized treatment, subject number and, when appropriate, by visit / date of assessment. If a listing includes non-randomized subjects, these will appear after the randomized subjects. All data collected are displayed, including unscheduled visits (if any).
- In summary tables and graphical representations, subjects are grouped by randomized treatment group, except for the SAF for which the actual treatment is used.
- In summary tables based on the RND, FAS, PPS and SAF, the order of the treatment groups is: placebo, ACT-132577 5 mg, ACT-132577 10 mg, ACT-132577 25 mg, ACT-132577 50 mg and Lisinpril 20 mg, followed by Total (if required). In summary tables based on the RIS or SCR, only a total column will be given.

- The absolute change from baseline to Visit X is defined as the difference between the post-baseline Visit X value and the baseline value.
- In order to analyze the data at the relevant planned (scheduled) visits, all recorded assessments for each subject up to the Week 10 visit are reassigned to the most appropriate visit according to the time window for that visit. The windows are consecutive (i.e., there are no gaps) and are based on the study day corresponding to the date of assessment. Any unscheduled visit is also mapped to a time window. Details of the visit mapping are given in Section 11.1.
- According to section 11.3.2.2 of the protocol, imputation rules for missing data are defined for the evaluation of efficacy endpoints at Week 8. Subjects without a value in the defined Week 8 time window are included in the analysis according to the rules highlighted in Section 9.

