10.9.4 Laboratory tests

All hematology and chemistry parameters provided by the central and local laboratory are displayed in a subject listing. Marked laboratory abnormalities will be flagged

accordingly. Laboratory values below the limit of detection (i.e., preceded by '<') will be replaced by half that limit in calculations as well as in determining abnormalities.

Hematology, chemistry and urine parameters UACR will be summarized by treatment group for each time window visit. Changes from baseline in these parameters will be summarized for each post-baseline assessment, displaying:

- observed values at baseline and at the post-baseline visit window
- absolute change from baseline to post-baseline visit window

In each evaluation only subjects who had both the assessments at baseline and the considered post-baseline time point are included.

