10.9.4.1 Treatment-emergent marked laboratory abnormalities

For each category (i.e., LL, LLL, HH, HHH, HHHH), treatment-emergent marked laboratory abnormalities [see definition in Section 5.6.8.1] will be summarized by treatment group, displaying counts and percentages of subjects with at least a treatment-emergent marked laboratory abnormality for each parameter for which the marked abnormality is defined. Values from unscheduled visits are included. Subjects may be included in more than one category for the same parameter.

In addition, the number of patients with $ALT > 3 \times$ upper limit of normal (ULN) and bilirubin $> 2 \times$ ULN will be tabulated by treatment group and time point (baseline, Week 8).

Percentages are calculated as number of subjects with at least one abnormality for the parameter under consideration divided by the number of subjects with any post-baseline laboratory measurement.

The distribution of the changes from baseline in hemoglobin will be plotted for each post-baseline visit. As an exploratory analysis, dose trends in the change from baseline to Week 8 in hemoglobin will be analyzed using the MCP-Mod approach. The active comparator will be excluded from these analyses.

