10.9.5 Physical examination, vital signs and body weight

Physical examination data performed during the course of the study will be reported in a subject listing. Pulse rate and body weight measurements will be reported in a subject listing and summarized by time window visit.

Furthermore, for each post-baseline assessment, average PR (from BpTRU[®]) and body weight will be summarized displaying, for each treatment group, descriptive statistics for:

- observed values at baseline and at the post-baseline visit window
- absolute change from baseline to post-baseline visit window

In each evaluation only subjects who had both the assessment at baseline and the considered post-baseline assessment are included. Only measurements obtained in sitting position will be taken into account.

The density of the changes from baseline in body weight will be plotted for each post-baseline visit. As an exploratory analysis, dose trends in the change from baseline to Week 8 in body weight ([kg]) will be analyzed using the MCP-Mod approach. The active comparator will be excluded from these analyses.

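### The exploratory Week 8 dose-response models for hemoglobin and body weight have no missing-data rule, so early stoppers fall out and the curves may be flattened at higher doses if stopping is related to these outcomes

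*SAP*

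**What the plan says.** SAP 4.1.3 adds two exploratory safety analyses. SAP 10.9.4.1 says that "dose trends in the change from baseline to Week 8 in hemoglobin will be analyzed using the MCP-Mod approach", and 10.9.5 says that "dose trends in the change from baseline to Week 8 in body weight ([kg]) will be analyzed using the MCP-Mod approach". SAP 13.11 and 13.12 assign both to the Safety Set, and lisinopril is excluded. Neither set of MCP-Mod outputs is flagged as key.

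- **Visit window.** In SAP 11.1, Table 5, Week 8 runs from Day 43 to the end of double-blind treatment. Values more than 25 hours after that end fall in the Visit 8 window.
- **Who is included.** For laboratory data, SAP 10.9.4 says "In each evaluation only subjects who had both the assessments at baseline and the considered post-baseline time point are included". For weight, SAP 10.9.5 says "In each evaluation only subjects who had both the assessment at baseline and the considered post-baseline assessment are included".
- **Missing data.** SAP 9.1 gives LOCF for analyses on the FAS, with BOCF and a mixed model as sensitivity analyses. SAP 10.2 limits the scope: "imputation rules for missing data are defined for the evaluation of efficacy endpoints at Week 8". Nothing is stated for the Safety Set.
- **Data collected.** Weight and laboratory tests are taken at Weeks 2, 4 and 8 (Protocol Table 1). They are also taken at a premature end-of-treatment visit within 7 days of the last dose (Protocol 8.4).
- **Stopping.** Protocol 5.1.12 D lists hemoglobin triggers, among them "A decrease in hemoglobin from baseline of > 50 g/L", and also allows stopping on the investigator's judgment. Protocol 5.1.11 lets the subject, investigator or sponsor stop treatment, for example after an adverse event. No stopping criterion is given for weight gain or fluid retention.

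**The concern.** A subject who stops before Day 43 gives no Week 8 value to either model, even though Week 2 and Week 4 values may exist. Phase 1 showed a treatment-related hemoglobin decrease and an apparent weight increase at 100 mg (Protocol 1.2.1). The Amendment 2 rationale (item 4) asks for "sufficient exposure to allow proper evaluation of the safety of the compound (e.g., fluid retention) in this indication". It is therefore plausible that some early stopping is related to the outcomes being modelled and is more frequent at higher doses. The models would then describe those who tolerated the drug, and the likely error is a flatter curve.

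These are the only modelled safety dose-responses in a study meant to find the doses with the best balance of efficacy and tolerability (Protocol 1.3). For blood pressure, SAP 9.1 acknowledges that Week 8 completers are a selected group, and the plan adds LOCF, BOCF and a mixed model. Hemoglobin and weight receive none of these.

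**Working it through.** **1. Who enters the models.** Take a subject who stops on Day 40 and attends the premature end-of-treatment visit on Day 45. The Week 8 window opens on Day 43 and closes at the end of treatment, here Day 40, so it is empty. The Day 45 value goes to the Visit 8 window. The subject drops out of both models. A subject who stops on Day 50 with a value on Day 45 stays in.

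**2. The plan's own figure.** The only related figure is the drop-out inflation in Protocol 11.5.1. 70/(1 − 0.20) = 88 per group against 90 stated, and 420/0.80 = 525 against 540 stated, so it reproduces approximately. The planned share outside the PPS is 1 − 420/540 = 22%. That covers every reason for exclusion and is not a rate of hemoglobin- or fluid-related stopping. The documents give no SD, effect or power for hemoglobin or weight, so everything below rests on assumptions.

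**3. The numeric hemoglobin stop alone.** Assume a mean fall of 5–15 g/L and an SD of 8–12 g/L. In the most unfavorable corner, t = (50 − 15)/12 = 2.92. The probability of a fall above 50 g/L is 1 − Φ(2.92) = 0.18%. Removing those subjects moves the arm mean by 12·φ(2.92)/(1 − 0.0018) = 0.07 g/L, which is negligible.

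**4. Upper bound.** If exactly the most extreme fraction f of one arm is lost, its mean moves by φ(z_f)/(1 − f) SD, where z_f is the normal quantile at f:

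| f | shift (SD) |
|---|---|
| 1% | 0.03 |
| 5% | 0.11 |
| 10% | 0.20 |
| 20% | 0.35 |

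**5. Graded dependence.** Assume 15% drop-out on placebo, a true 50 mg minus placebo difference of 1 SD, and log-odds of drop-out that rise linearly with the subject's own change:

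| rise in log-odds per SD | drop-out at 50 mg | share of true difference retained |
|---|---|---|
| 0 | 15% | 100% |
| 0.25 | 18% | 99% |
| 0.5 | 22% | 97% |
| 1.0 | 29% | 88% |
| 1.5 | 35% | 80% |

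The last two rows need more loss at 50 mg than the roughly 20% drop-out the protocol plans for.

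**6. Scale for weight.** Assume an SD of 1.8 kg, a true difference of 1.2 kg, about 8% random loss, and stopping with probability 0.5–0.8 above +2.5 to +4 kg at Week 2 or 4. Simulated observed Week 8 differences were 0.97–1.16 kg, that is, 3–19% too small or 0.04–0.23 kg. The SE of a two-arm difference is 1.8·√(2/n). It is 0.30 kg at n = 70 and 0.28 kg at n = 82 (490/6, from the re-estimated size in SAP 4.2). The shortfall is below one SE.

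**The case against.** A reader might infer that the dose effect on safety *is* understated. The documents do not support that, for four reasons.

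- No rate of hemoglobin- or fluid-related stopping is given, and with unrelated stopping there is no bias.
- The numeric hemoglobin rule is too extreme to matter, and there is no stopping rule for weight. Any effect must come through adverse events or through investigator or subject decisions.
- Only two exploratory, non-key analyses are affected. By-visit summaries use the Week 2 and 4 values. Marked laboratory abnormalities count any value up to 30 days after double-blind treatment. Adverse events leading to discontinuation are tabulated by arm.
- The sentences on paired assessments are written for the descriptive summaries, so applying them to MCP-Mod is an inference.

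A reader might also take a simulated recovery of the true 1.20 kg by a mixed model as proof that the remedy works. It is not proof. In that simulation drop-out depends only on observed Week 2 and 4 values, so recovery follows by construction.

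All of this stands, and it limits the claim to a possible bias of unknown size. It does not remove the gap: no other rule exists for these two models, the by-visit and event tables do not estimate a dose-response curve, and the marked-abnormality table (SAP Table 2) has no weight threshold.

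**Conclusion.** The point holds in limited form. The plan leaves the handling of missing Week 8 hemoglobin and weight unstated. Read with the visit windows, it excludes subjects without a value from Day 43 to the end of treatment. If early stopping is related to these outcomes, the two curves may be flattened at the higher doses. The loss is zero under unrelated stopping, about 1–3% of the high-dose difference under mild dependence, and 12–20% under strong dependence. These figures depend on the assumed drop-out model and not on trial data. The upper end requires 29–35% loss at 50 mg. The primary endpoint, alpha and sample size are untouched. This is a cheap improvement to two exploratory analyses and does not threaten the trial's main conclusion.

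**What to change.** For hemoglobin and body weight, fit the *Last time point* mixed model of SAP 9.3. It uses Weeks 2, 4 and 8, with treatment, week, treatment by week, baseline and baseline by week, and an unstructured covariance. Include Safety Set subjects on placebo or ACT-132577 with at least one on-treatment post-baseline value. Pass the Week 8 LSMeans and their covariance to the general MCP-Mod. State the direction explicitly: `increasing` for weight and `decreasing` for hemoglobin. The SAP 9.2 code sets `decreasing` for blood pressure, and no direction is given for these two variables.

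Report this alongside the observed Week 8 analysis and an analysis of the last on-treatment value. Show the number missing Week 8 in each arm.

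The cost is a few lines of SAP text and another run of existing code. The downside is that the model relies on missing at random given the Week 2 and 4 values. Stopping because of a change that arises after the last attended visit would still bias it, which is why the other two analyses should sit beside it.

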10.9.6 Other safety variables

Not applicable.

10.10 Analysis of quality of life variables (TSQM vII)

Not applicable.

10.11 Analysis of pharmacoeconomic variables

Not applicable.

10.12 Analysis of epidemiological measures and risk-benefit evaluations

Not applicable.

10.13 Analysis of pharmacodynamic variables

For the analysis of ET-1 the PK set will be used. ET-1 plasma concentrations will be summarized by active treatment and visit by arithmetic mean, SD of the mean, minimum, maximum, median, coefficient of variation of the arithmetic mean (CV%), and number of observations. A subject listing presenting ET-1 data will also be provided. Data presentations will follow the general rules as described in Section 10.2.

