5.1.1 Investigational treatment: description and rationale

Four fixed doses of ACT-132577 (5 mg, 10 mg [2 \times 5 mg], 25 mg, and 50 mg) covering a dose range of 10-fold are selected for the present dose finding study. The study treatment must be taken orally o.d. based on the PK profile of ACT-132577 ($t_{1/2}$ of approximately 44 h). ACT-132577 can be administered irrespective of food as the PK of ACT-132577 were not affected by food [ACT-132577 IB].

In the AC-080-101 Phase 1 study, a dose-dependent increase in ET-1 plasma concentrations was observed after several days of treatment up to the highest tested dose of 100 mg ACT-132577.

At a dose of 5 mg, ET-1 plasma concentrations did not differ from subjects treated with placebo, whereas 25 mg induced a clear increase in ET-1 plasma concentration. Therefore, 5 mg and 10 mg are selected to cover the lower-part of the dose-response curve. 25 mg and 50 mg are selected to complete the dose-response curve. The exposure margins and the nonclinical safety program support this Phase 2 clinical trial at doses up to 50 mg o.d. for a treatment period of 8 weeks [ACT-132577 IB].

Essential hypertension Protocol AC-080A201 Version 3 30 May 2016, page 43/112

Confidential

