7.4 Pharmacokinetic and pharmacodynamic assessments

Blood samples for determination of PK and PD will be collected for all subjects to provide information about the concentration of the drug in the target population and its effect on the PD marker ET-1. Blood samples will be drawn at trough (before morning dose) at Week 2 (Visit 5), Week 4 (Visit 6) and Week 8 (Visit 7).

No genetic analysis will be conducted.

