11.3.6 Analysis of other variable(s)

PK and PD data will be listed by subject number and PK endpoints will be analyzed descriptively by treatment. PK trough and ET-1 plasma concentrations at each visit will be summarized by treatment using arithmetic mean, minimum, median, maximum, standard deviation (SD), standard error, and two-sided 95% CI of the mean.

If possible, the exploratory PK/PD analysis will be performed in which the relationship between ACT-132577 plasma concentrations and ET-1 levels is investigated.

Whenever possible, a model will be established to describe these relationships. Exploratory data-driven analysis may be performed, with the caveat that any statistical inference will not have any confirmatory value. The results of this analysis will be reported separately.

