5.9 Pharmacodynamic variables

Trough plasma concentrations of ET-1, measured at steady state at Weeks 2, 4 and 8 in DB treatment period (Period II). Trough is defined as a sample taken in the morning of the visit prior to study treatment administration of that visit.

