7.1.7 Pharmacokinetic Set

The PK Set includes all subjects from the PPS who had at least one evaluable PK trough sample. Subjects are evaluated according to the study treatment they have received.

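### The SAP's ET-1 summary, read literally, omits placebo although placebo is sampled, no baseline ET-1 exists and the protocol plans the summary by treatment, so the ET-1 effect over placebo cannot be read from it

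*SAP*

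**What the plan says.** **SAP.** Section 10.13 sets the population, "For the analysis of ET-1 the PK set will be used", and the grouping, "ET-1 plasma concentrations will be summarized by active treatment and visit". The statistics listed are arithmetic mean, SD, minimum, maximum, median, CV% and number of observations, plus a subject listing. Section 7.1.7 defines the population: "The PK Set includes all subjects from the PPS who had at least one evaluable PK trough sample". Section 5.9 gives the ET-1 time points as Weeks 2, 4 and 8 of the double-blind period. Section 13.14.2 plans one table (PD1) and one listing (PDTROUGH), both on the PK Set.

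**Protocol.** Section 11.3.6 plans a wider summary: "PK trough and ET-1 plasma concentrations at each visit will be summarized by treatment". Its statistics include the standard error and a two-sided 95% CI of the mean. Section 11.1.6 assigns the PK Set to pharmacokinetic analyses and names no set for ET-1. Section 7.4 states that "Blood samples for determination of PK and PD will be collected for all subjects" and gives as one purpose to learn the drug's effect on ET-1. Table 1 and Section 7.3.5.2 place the PK/PD sample at Visits 5, 6 and 7 only.

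**Declared changes.** SAP 4.1 covers analysis sets, secondary efficacy and safety. It says nothing about the ET-1 summary.

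**The concern.** ET-1 is an endogenous marker, so a level on drug means little without a level off drug. This trial has two possible sources for that reference: a pre-dose sample in the same subject, or the concurrent placebo group. The first was never planned. The second is collected but, under SAP 10.13 as worded, not tabulated.

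The sponsor's own dose rationale uses this comparison. Protocol 5.1.1 reports from Phase 1 that "At a dose of 5 mg, ET-1 plasma concentrations did not differ from subjects treated with placebo", whereas 25 mg gave a clear increase, and it places 5 and 10 mg on the lower part of the curve on that basis. Whether that pattern holds in hypertensive subjects is an obvious use of these samples, and the planned table would not show it.

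The phrase looks carried over from SAP 10.14, which groups the drug concentrations in the same way under an explicit limit to the ACT-132577 groups; tables PK1 and PD1 also share a mock layout. Leaving placebo out is sensible for drug concentration. It is not sensible for a marker that placebo subjects also have.

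**Working it through.** The documents give no sample size, power or precision figure for ET-1, so there is no stated figure to reproduce. The check has two parts.

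**1. The texts side by side**

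| Item | Protocol | SAP |
|---|---|---|
| Grouping of ET-1 | by treatment (11.3.6) | by active treatment (10.13) |
| Population | none named for ET-1 | PK Set (10.13) |
| Precision | SE and 95% CI of the mean (11.3.6) | SD, CV% and n; no SE or CI (10.13) |
| Subjects sampled | all (7.4) | not restated |
| Time points | Weeks 2, 4, 8 (6.3.2, 7.4) | Weeks 2, 4, 8 (5.9) |
| Narrowing declared | – | not in 4.1 |

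The general rules do not clearly bring placebo back. The column order in SAP 10.2 that starts with placebo is stated for the RND, FAS, PPS and SAF, not the PK Set, and applies unless otherwise specified. Lisinopril is unclear too: it is the active reference, so *active treatment* may or may not include it.

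Scale: SAP 4.2 gives 490 randomized in six equal groups, so 490 / 6 = 81.7, about 82 on placebo. The sample-size re-estimation SAP expects the PPS to be at least 80% of the FAS. With FAS close to randomized and equal loss across groups, 0.80 × 81.7 gives about 65 placebo subjects in the PPS.

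**2. What the four doses still show**

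Assume, for illustration only, that ET-1 follows one of the six blood-pressure candidate shapes in SAP 9.2 (Table 3 starting values, log offset 0.5), with equal groups and equal variance. Only ratios are used, so no ET-1 SD is needed. For a shape f:

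- S5 = Σ(f(d) − mean)² over 0, 5, 10, 25, 50 mg; S4 = the same over 5, 10, 25, 50 mg.
- Share of dose-trend information kept = S4 / S5.
- Inflation of the trend's standard error = √(S5 / S4).
- Visible share of the effect = [f(50) − f(5)] / [f(50) − f(0)].

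Linear shape in full: the mean of the five doses is 18, so S5 = 324 + 169 + 64 + 49 + 1024 = 1630. The mean of the four is 22.5, so S4 = 306.25 + 156.25 + 6.25 + 756.25 = 1225. Kept: 1225 / 1630 = 0.75. SE inflation: √(1630 / 1225) = 1.15. Visible share: 45 / 50 = 0.90.

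| Shape | Information kept | SE inflation | Visible share, 5 to 50 mg |
|---|---|---|---|
| Logistic | 0.77 | 1.14 | 0.91 |
| Linear | 0.75 | 1.15 | 0.90 |
| Quadratic | 0.70 | 1.19 | 0.87 |
| Emax | 0.63 | 1.26 | 0.82 |
| Sigmoidal Emax | 0.27 | 1.93 | 0.52 |
| Linear in log | 0.23 | 2.1 | 0.48 |

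The loss is modest if the marker rises steadily with dose and large if much of the rise occurs by 5 mg. Without placebo the table cannot tell these cases apart.

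**The case against.** **The data are not lost.** Placebo samples are taken, the PK Set does not expressly exclude placebo, and the only deviation that SAP Section 6 ties to exclusion from that set is a sample not taken at trough. SAP 10.14 has to state its restriction to ACT-132577 groups, which suggests that the set itself carries none. The titles of PD1 and PDTROUGH name no restriction either. All of this stands, so a reader who infers that all reference information for ET-1 is lost goes too far. What remains is that the sentence defining the summary says active treatment, and *evaluable* is not defined for a placebo or lisinopril PK sample.

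**A dose effect is still visible.** A reader might infer that no dose effect on ET-1 can be read. The documents do not support that: four randomized doses over a 10-fold range appear side by side by visit. Only the comparison with no drug is missing.

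**The objectives do not ask for placebo.** Protocol 2.3 and SAP 3.3 ask for steady-state trough ET-1 and its correlation with drug concentration. This is correct, so it cannot be said that a stated objective becomes unanswerable, or that a planned ET-1 dose-response analysis loses a group; no such analysis is planned. Protocol 7.4 does, however, name the effect on ET-1 as a reason for sampling.

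**The PK Set matters little.** PK and ET-1 plasma come from one procedure and are split into two tubes (Protocol 7.4.1), so few subjects should have one without the other. This largely stands; the set matters mainly through the undefined status of placebo samples.

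**The CI can be derived.** SD and n give it for any group tabulated. True, but not for a group left out.

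**Other references exist.** Lisinopril is sampled but is an active drug. The Phase 1 finding at 5 mg comes from healthy subjects, with six on active drug in the multiple-dose group, and 10 mg was not among the Phase 1 doses (Protocol 1.2.1).

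**Conclusion.** The point holds as a reporting defect with a narrow consequence. As worded, SAP 10.13 replaces a protocol summary by treatment with one by active treatment, does not declare the change, and leaves an ET-1 table with no untreated reference in a trial that has no baseline ET-1. The effect over placebo, and whether 5 or 10 mg raises ET-1 in this population, cannot be read from that table. Comparisons among the four doses can.

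The size depends on an unknown shape: 23% to 77% of the dose-trend information is kept, the trend's standard error is 1.14 to 2.1 times larger, and 48% to 91% of the 0-to-50 mg effect stays visible. These ranges borrow the blood-pressure candidate shapes and assume equal groups and equal variance. The conclusion itself needs only the literal reading of 10.13 and the absence of a pre-dose sample.

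ET-1 belongs to the other objectives and its analysis is descriptive. SAP 10.1 treats everything beyond the main analysis as exploratory. No primary or secondary result is affected.

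**What to change.** In SAP 10.13 and table PD1:

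- Summarize ET-1 by visit for all six randomized groups, including placebo and lisinopril.
- Use PPS subjects with an evaluable ET-1 trough sample, whether or not the PK sample is evaluable. Apply the same population to listing PDTROUGH.
- Restore the protocol's two-sided 95% CI of the mean.
- Optionally, add a descriptive difference from placebo per dose and visit. The protocol does not plan this, so it should be labelled exploratory.

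If the sponsor prefers to keep the active groups only, SAP 4.1 should list the change from Protocol 11.3.6 with a reason, and 10.13 should say whether lisinopril is included.

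The cost is a few extra columns and one added statistic in a single exploratory table. The samples are already planned for all subjects.
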